APPENDIX 3 INTERPRETATION OF HEPATITIS B SEROLOGICAL TEST RESULTS

As our study drug is expected to demonstrate immunosuppressive effects, we find it necessary to carefully evaluate and exclude subjects with potentially active Hepatitis B infection. For this reason, in order to fully evaluate subject's eligibility for enrollment, Exclusion Criterion 3f requires interpretation of data from three standard tests for hepatitis B i.e. measurement of hepatitis B surface antigen (HBsAg), hepatitis B surface antibody (anti-HBs) and Hepatitis B core antibody (anti-HBc).

Subject's eligibility for enrollment should be assessed as described below:

- Subjects that are negative for all three markers are allowed into the study
- Subjects that are HBsAg (neg), anti-HBc (neg) and anti-HBs (pos) are allowed into the study (immunized subjects)
- Subjects that are HBsAg (neg), anti-HBc (pos) and anti-HBs (pos) are allowed into the study (Hep B immune most likely due to natural exposure)
- Subjects that are HBsAg (pos) are excluded from the study
- Subjects that are HBsAg (neg), anti-HBc (pos) and anti-HBs (neg) may be included after additional discussion with Medical Monitor in order to evaluate subject's full clinical status and medical history.

Please also refer to the below "Interpretation of Hepatitis B Serologic Test Results" provided by the Department of Health and Human Services, CDC.

8 CONTENT OF REPORTS23

LIST OF TABLES

Table 4.3-1: Commonly Used PK Parameters, Naming Conventions and
Definitions.....9
Table 6.2-1: Treatment Group.....10
Table 7.7-1: PK Sample Study Day and Time17

LIST OF FIGURES

Figure 2.1-1: Study Design Schematic6
Figure 2.1-2: Decision Rule on Intra-Subject Dose Escalation7

Schedule of Analyses:

[figure not shown]
- Interim analysis may be performed repeatedly with accumulating data, perhaps without formal database lock, to provide an intermittent dose.
- Final CSR reports will be provided with formal database lock.

2 STUDY DESCRIPTION

2.1 Study Design

This is a Phase 1b/2, multicenter, open-label, MAD study to evaluate the safety, efficacy, dose response, and pharmacology (PK, target engagement and PD) of BMS-986004 administered every 2 weeks in subjects with ITP.

Figure 2.1-1: Study Design Schematic

[figure not shown]
The study is divided into screening (3 weeks), response phase (6 weeks), remission phase (6 weeks) and follow up period (4 weeks). Forty subjects are treated in 4 dose panels, 75mg, 225mg, 675mg, and 1500mg, of 10 subjects each. BMS-986004 will be administered on day 1, 15, 29, 43, 57, 71, 85, a total of 7 doses as IV infusion. Four (4) doses will be administered during the Response Phase over a 6 week treatment period. The remaining 3 doses will be administered during the Remission Phase of the study over a 6 week treatment period. The study design schematic is presented in Figure 2.1-1.

Cohort of lower than 75mg or intermittent dose may be opened.

Intra-subject dose escalation

Subject may be dosed at a higher dose beginning from day 57 for the remainder of the study if clinically significant response has not been achieved at Day 43 and Day 50, and a favorable safety profile is observed.

Figure 2.1-2: Decision Rule on Intra-Subject Dose Escalation

2.2 Treatment Assignment

Interactive Voice Response System (IVRS) will be used for assignment of subject number and cohort.

2.3 Blinding and Unblinding

Not applicable.

2.4 Protocol Amendments

This analysis plan reflects all protocol amendments through Amendment 02, dated 31-Jul-2014.

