Amendment 02	31-Jul-2014	The purpose of this amendment is to provide clarification and consistency on various sections in the protocol: for consistency, upper limit of age has been updated in some sections of the protocol to > 18 years old, early decision for dose escalation section has been updated and correction has been made to method of assigning subject identification section. In addition, some typographical edits, format updates and clarifications are made throughout the protocol.
Original Protocol	20-Jun-2014	Not applicable

SYNOPSIS

Clinical Protocol IM140103

Protocol Title: Open Label, Adaptive Design, Ascending, Multiple-Dose Study to Evaluate Safety and Efficacy of BMS-986004 in Adult Subjects with Primary Immune Thrombocytopenia (ITP)

Investigational Product(s), Dose and Mode of Administration, Duration of Treatment with Investigational Product(s): Total of 40 subjects will be enrolled for the study, treated in dose panels of 10 subjects each. Four (4) dose panels are planned to be enrolled sequentially in an ascending manner, with dose intensity selected to provide increased levels of immunosuppression at steady state. Dose levels that are planned to be evaluated in this trial are expected to elicit a range of clinical response. Based on current preclinical projections, the doses range from 75 mg to 1500 mg every two weeks.

BMS-986004 will be administered once every 2 weeks as an IV infusion for a total of 7 doses. Subjects will receive investigational product on Day 1/Week 0, Week 2, Week 4, Week 6, Week 8, Week 10 and Week 12, for a total of 7 doses.

During the long term extension (LTE) period, BMS-986004 will be administered once every 2 weeks as an IV infusion for 24 weeks and during 2 Taper visits.

Study Phase: Phase 1b/2

Research Hypothesis: Because current study is an open label trial without placebo control, there is no formal research hypothesis to be statistically validated. The purpose of this study is to test if BMS-986004 will be effective in normalizing platelet counts in subjects with ITP, as well as to assess the safety, PK and immunogenicity of multiple doses of BMS-986004 in ITP subjects.

Primary Objectives:

- To assess the overall safety and tolerability of multiple doses of BMS-986004, when administered in subjects with chronic ITP.

Secondary objectives:

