3 INVESTIGATIONAL PLAN

3.1 Study Design and Duration

This is a Phase 1b/2, multicenter, open-label study to evaluate the safety, efficacy, dose response, and pharmacology (PK, target engagement and PD) of BMS-986004 in subjects with ITP.

The study will comprise a short-term period and a long term extension (LTE) period.

The short-term period, is divided into three phases: Response Phase (6 weeks), Remission Phase (6 weeks) and Follow Up phase (8 weeks).

Screening evaluations to determine subject eligibility will be performed 21 days prior to study drug administration. The screening period may exceed 21 days but not more than 42 days total, and only after a discussion with and approval by the Study Director. If an extension in screening time is granted, the patient must still follow the platelet count rules for enrollment. The baseline platelet count determining enrollment eligibility will be based on the mean of two determinations taken within a week of the first dose. To be eligible for enrollment, platelet count needs to be less than $30,000/\text{mm}^3$ and show stable or declining trend. If the mean platelet count is between $30,000 - 35,000/\text{mm}^3$ the subject may be considered for enrollment on a case by case basis after discussion with and approval by the Study Director.

Following screening, a total of 40 evaluable subjects are planned for the study. Subjects are considered evaluable if they receive the first 4 doses of study drug and complete the required

safety and efficacy evaluations at Day 50. Non-evaluable subjects will be replaced to maintain a count of 10 subjects in each dose panels, except subjects will not be replaced if they are discontinued from the study secondary to an adverse event unless the adverse event can be determined to be unrelated to treatment.

Subjects are treated in dose panels of 10 subjects each. Four (4) dose panels are planned to be enrolled sequentially in an ascending manner, with dose intensity selected to provide increased levels of immunosuppression at steady state. Dose levels (range from 75 mg to 1500 mg administered every two weeks) that are planned to be evaluated in this trial are expected to elicit a range of clinical response.

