The approximate duration of the long term extension is approximately 55 weeks. This includes 24 weeks of every other week dosing of 1500 mg, two-taper visits (7 weeks total), and a 24 week follow-up period (no treatment).

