6 STUDY PERIODS, TREATMENT GROUPS AND POPULATIONS FOR ANALYSES

6.1 Study Periods

The approximate duration of the study is 20 weeks (approximately 140 Days). This includes a 21 day screening period, a 12 week treatment period (6 weeks of response Phase and 6 weeks of remission phase) and a 1 month follow up period. The end of study will be defined as the date of the last visit of the last subject undergoing the study.

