6.2 Treatment Groups

Treatment groups will be decided by the planned starting dose regardless of intra-subject dose escalation planned at day 57. Table 6.2-1 below indicates the planned treatment groups.

All summaries, except PK summary, will be provided by treatment group. For PK summary, it is current dose that is used to decide the dose group.

Table 6.2-1: Treatment Group

Cohort	Treatment Group Label
A	BMS 75mg
B	BMS 225mg
C	BMS 675mg
D	BMS 1500mg

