7.5.4 Response with primary efficacy criteria

The best response status over the entire study will be reported for all treated subjects with platelet at baseline, administered dose on day 1, and administered dose on day 57. For responders, treatment group, dose escalation status (Y/N), time to respond, time to peak response, and duration of response will be provided in a listing.

Response rates and number of subjects having dose escalated will be provided for each treatment group and all.

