7.6 Safety

Analysis of safety will be based on All Treated Subjects and presented by treatment (“as treated”) and overall.

Adverse events (AEs) will be coded according to the most current version of MedDRA and be graded using the NCI Common Terminology Criteria for Adverse Events (CTCAE) version 4.0. Drug-related AEs are those events with relationship to study drug “Related” as recorded on the CRF. If the relationship to study drug is missing, the AE will be considered as drug-related.

Listing of adverse events will include all enrolled subjects as SAEs and deaths are collected pretreatment. Summaries of adverse events will include (1) events occurring from the first dose date to 35 days (inclusive) after the last dose of BMS-986004 for subjects who are off study

treatment and (2) all events occurring from first dose date for subjects who are still on study medication.

When reporting adverse events by CTC grade, summary tables will be provided based on the event with worst CTC grade (independent of relationship to study medication). Subjects will only be counted (1) once at the preferred term (PT) level, (2) once at the system organ class (SOC) level, and (3) once in the 'Total subject' row at their worst CTC grade, regardless of SOC or PT.

The analysis of laboratory results will be based on All Treated Subjects. Laboratory results will be categorized according to NCI CTCAE (version 4.0) grade. Baseline is defined as the last non-missing measurement prior to the first dosing date and time. Summaries of laboratory results include baseline and (1) post-baseline results up to 35 days (inclusive) after the last dose of BMS-986004 for subjects who are off study treatment and (2) all available post-baseline results for subjects who are still on study medication.

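### The SAP has no long-term extension, so its AE and laboratory window, taken literally, runs up to 217 days longer in cohorts C and D than in A and B

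*SAP*

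**What the plan says.** **SAP**
- Section 2.4: "This analysis plan reflects all protocol amendments through Amendment 02, dated 31-Jul-2014". The protocol's document history describes that amendment thus: "The purpose of this amendment is to provide clarification and consistency on various sections in the protocol". It lists no LTE among the changes.
- Section 6.1 gives about 20 weeks in total, with "a 1 month follow up period". No LTE period, population or endpoint appears in the SAP.
- Section 7.6 summarises events "from the first dose date to 35 days (inclusive) after the last dose of BMS-986004" for subjects off treatment, and all events since first dose for subjects still on drug. Laboratory results follow the same rule.
- Section 6.2: "Treatment groups will be decided by the planned starting dose regardless of intra-subject dose escalation". This governs every summary except PK. Section 7.6, however, says that safety is presented as treated.
- Section 7.5.4: "The best response status over the entire study will be reported for all treated subjects".

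**Protocol**
- Section 3.1 has a "Follow Up phase (8 weeks") and limits the LTE to cohorts 3 and 4.
- The duration text at the end of 3.1.4 says of the LTE: "This includes 24 weeks of every other week dosing of 1500 mg". Two taper visits follow, with the last dose on LTE Day 218 (3.1.5). Table 5.1-3 equates LTE Day 1 with Day 85.
- Section 5.3 summarises treatment-emergent events from first dose through Study Day 85.
- Sections 8.2 and 8.4.8 give the LTE its own population and descriptive analyses. Section 8.3.4 says that LTE safety is assessed cumulatively, without naming the starting day.

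**The concern.** Adverse events and laboratory abnormalities are the primary endpoints, tabulated as crude incidence by cohort. A window tied to the last dose of drug was harmless while every subject's last planned dose fell on Day 85. Once some subjects in two of the four cohorts can go on dosing for another 31 weeks, the same words give different follow-up by cohort. The longer follow-up falls on the two highest starting doses, so an artefact of time would look like a dose effect.

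For cohort C there is a second problem: events during months at 1500 mg would stand under the 675 mg label.

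**Working it through.** **1. The protocol's own LTE figure.** 24 weeks of dosing + 7 weeks of taper + 24 weeks off drug = 55 weeks, as stated. By visit days, (169 − 1)/7 = 24.0 weeks of two-weekly dosing, (218 − 169)/7 = 7.0 weeks of taper, and (218 − 1)/7 = 31.0 weeks from LTE Day 1 to the last dose.

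**2. End of the SAP 7.6 window.**
- No LTE: last dose Day 85, so 85 + 35 = Day 120.
- LTE completer: last dose 85 + 217 = Day 302, so 302 + 35 = Day 337.
- Difference: 337 − 120 = 217 days = 31.0 weeks. Ratio: 337/120 = 2.8.
- Check against the exposure formula in SAP 7.6.5 (last dose − first dose + 35 + 1): 84 + 36 = 120 days and 301 + 36 = 337 days.
- Against protocol 5.3 (Day 85), the SAP window is 35 days longer without the LTE and 337 − 85 = 252 days longer with it.

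**3. What falls inside the longer window.** After Day 85 an LTE completer receives 12 two-weekly and 2 taper doses, 14 in all, each of 1500 mg. Scheduled laboratory visits after Day 1 are 13 through Day 85. A subject without the LTE adds Days 99 and 113, making 15. An LTE completer adds 12 + 2 LTE visits and LTE Day 248 (85 + 247 = Day 332), making 28. SAP 7.6.7 reports the worst grade per subject, which can only rise with more visits.

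**4. Effect on crude incidence.** Neither the hazard nor LTE uptake is given in the documents, so both are assumed: a constant hazard, and a share f of the cohort that enters and completes the LTE. If p is the incidence by Day 120, a completer has p_L = 1 − (1 − p)^(337/120), and the cohort shows (1 − f)p + f·p_L.

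| p by Day 120 (A and B unchanged) | LTE completer | Cohort, f = 30% | Cohort, f = 70% |
|---|---|---|---|
| 10% | 25.6% | 14.7% | 20.9% |
| 20% | 46.6% | 28.0% | 38.6% |
| 40% | 76.2% | 50.9% | 65.3% |

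**5. Response.** Standard LTE entry needs at least 35,000/mm³ and a doubling from baseline (protocol 3.3.4), so these subjects already meet the platelet part of R. The SAP also requires zero SMOG scores on the day of the count (7.5.1), and Table 5.1-3 has no ITP-BAT row, so R and CR cannot be derived at LTE visits under that definition. The R/CR rate can therefore hardly move.

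If the entire study were read to include the LTE, platelet observation after Day 85 would be 397/7 = 56.7 weeks against 56/7 = 8 weeks, with 33 against 17 scheduled visits after Day 1. Time to peak, duration of response and percent of visits above a threshold could then change. So could upgrades from R to CR, if the bleeding condition were met by some other means.

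**The case against.** The strongest reply is that the protocol already separates the periods: a Day 85 cut-off for treatment-emergent events, response rate by response and remission phase (8.4.2), and a distinct LTE population. The SAP, for its part, was written for a 20-week study with seven doses, so its last dose means dose 7 and its entire study means those 20 weeks. On that reading no LTE data enter the short-term tables.

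This stands in part. It makes the bias conditional on following the SAP's words literally, and it is a natural reading of the best-response rule. It does not settle the safety window. SAP 7.6 names the last dose of the drug, has an open-ended branch for subjects still on drug, and differs from protocol 5.3 even without the LTE (Day 120 against Day 85). SAP 7.2 says that changes from protocol-specified analyses will be defined in the SAP, so a reader may take the SAP window as the intended one.

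Other replies also hold in part. Rates per 100 patient-years (SAP 7.6.5) adjust for time, but not for dose, and only in that one analysis. The as-treated wording in 7.6 leaves the label unsettled, but no rule is given for splitting a subject's time. The study tests no formal hypothesis, but the cohort tables are its main safety result.

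A reader might go further and infer the following, which the documents do not support:
- *An artificial gradient in response rate.* See step 5.
- *A bias that rises with cohort number.* A equals B, and C and D share one eligibility rule, so it is a step.
- *A wrong dose label in both cohorts.* Cohort D's planned dose equals the LTE dose; there the problem is time only, unless its dose was lowered.
- *20% becoming 47% in a cohort.* That figure is for an LTE completer.
- *Days 127 and 141 missing from every SAP schedule.* This can be checked only for PK Table 7.7-1, which ends 672 hours after Day 85 (Day 113). The platelet schedule is not visible.

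**Conclusion.** The point holds as an unreconciled conflict between the two documents on the window of the primary endpoint. Taken literally, the SAP adds up to 217 days to the adverse-event and laboratory window of LTE entrants, who come only from cohorts C and D. Crude incidence would then not be comparable between A/B and C/D. A 20% incidence by Day 120 would read as about 28 to 39% in C or D. This assumes a constant hazard and that 30 to 70% of the cohort enters and completes the LTE; shorter stays give less. The R/CR rate is little affected.

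That the LTE was added after Amendment 02 is a strong inference, since part of the document history is not available. A later SAP addendum or the data presentation plan might already deal with the matter; neither is among the documents. As the SAP stands, it should be corrected before the short-term safety tables are produced.

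**What to change.** Amend the SAP as follows.

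1. Use one common short-term cut-off for adverse-event and laboratory summaries in all cohorts, such as the protocol's own Day 85. Summarise later follow-up events in subjects who do not enter the LTE separately. State which table takes an event on Day 85 itself, which for entrants is also LTE Day 1.
2. State that best response, time to response, time to peak, duration and percent of visits use the short-term period, with the same cut-off in every cohort.
3. Summarise LTE data separately on the LTE Analysis Population.
4. Reconcile protocol 5.3 and 8.3.4 (cumulative from which day) with SAP 6.2 and 7.6 (starting dose or as treated). Update the SAP to 8 weeks of follow-up and add Days 127 and 141 to the PK table. Table 5.1-3 treats the Day 85 and LTE Day 1 doses as the same, although a cohort C subject's short-term dose may differ from 1500 mg; those passages also need reconciling.

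Stopping at Day 85 for LTE entrants but at 35 days after the last dose for everyone else would not do. It replaces one imbalance with another: under the same constant hazard, 20% by Day 120 is 1 − 0.8^(85/120) = 14.6% by Day 85, so C and D would look safer.

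The cost is a SAP amendment, with no new data. The downside is that events after the cut-off move to separate tables, so the short-term tables show fewer events.

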3 OBJECTIVES

3.1 Primary Objective

The primary objective of this study is to assess the overall safety and tolerability of multiple doses of BMS-986004, when administered in subjects with chronic ITP.

3.2 Secondary Objective

The secondary objectives are as follows.

- To evaluate efficacy of BMS-986004 in the treatment of thrombocytopenia in subjects with chronic ITP, as measured by platelet response/complete response (R/CR) and other clinical parameters.
- To establish BMS-986004 dose response, as measured by platelet count and other clinical parameters.

- To measure the target engagement of BMS-986004 following multiple IV doses
- To assess the effect of BMS-986004 on markers associated with the risk of thromboembolism (TE) in the multiple dose setting.
- To assess pharmacokinetics and immunogenicity of multiple doses of BMS-986004 in subjects with chronic ITP.

[REDACTED]

[REDACTED]

[REDACTED]

[REDACTED]

[REDACTED]

4 ENDPOINTS

4.1 Efficacy Endpoints

The first secondary objective of efficacy will be measured by the following efficacy endpoint:

- Response Rate (RR): Response rate is defined as the proportion of subjects who are responders.
- Time to Response: It is defined as the time, in weeks, from the first dosing day until the criteria for PR or CR are first met, whichever occurs earlier. Non-responders will be censored on the date of their last platelet measurement.
- Duration of Response: Duration of response is defined as the time, in weeks, from the first day when the criteria are met for PR or CR, whichever occurs first, until the date of disease progression. Subjects who do not progress will be censored on the date of their last platelet measurement. It is defined for responders only.
- Time to Peak Response: It is defined as the time, in weeks, from the first dosing day until the largest platelet count is met. It is defined for responders only.

4.2 Safety Endpoints

Safety endpoints include incidence of AE at the highest grade, death as well as marked abnormalities in clinical laboratory tests, vital sign measurements, ECGs, and physical examinations. Incidence of AEs is provided separately for overall AEs, serious AEs, and AEs leading to discontinuation.

4.3 Pharmacokinetic Endpoints

Pharmacokinetic parameters of BMS-986004 will be derived from serum concentration versus time data by analyte and collection interval. Individual pharmacokinetic parameter values will be derived by non-compartmental methods by a validated pharmacokinetic analysis program using actual times.

Table 4.3-1: Commonly Used PK Parameters, Naming Conventions and Definitions

Parameter	Definition
Cmax	Maximum observed serum concentration
AUC(TAU)	Area under the concentration time curve in one dosing interval
Ctrough	Trough observed concentration
CLT	Total body clearance
AI_AUC	AUC Accumulation Index; ratio of AUC(TAU) at steady state to AUC(TAU) after the first dose
AI_Cmax	Cmax Accumulation Index; ratio of Cmax at steady-state to Cmax after the first dose

4.5 Immunogenicity Endpoints

Immunogenicity endpoint is proportion of subjects by subject ADA status, which includes positive at baseline, subject ADA positive (further divided into persistent positive, not persistent positive but with the last sample positive, and other positive), and subject ADA negative.

Below given are the definitions of various sample ADA status and afore mentioned subject ADA status. The definitions are current as of the time when this SAP was drafted and are consistent with the recommendations from internal immunogenicity council. In case any of the definitions be changed or new category added, the SAP won't be amended, and the data presentation plan (DPP) will be updated.

ADA Status of a Sample:

- Baseline ADA Positive Sample: ADA is detected in the sample before initiation of treatment
- ADA Positive Sample: After initiation of treatment, (1) an ADA positive sample in a subject who is baseline ADA negative, or (2) an ADA positive sample with ADA titer to be at least 9-fold or greater (\geq) than titer of a baseline ADA positive
- ADA Negative Sample: After initiation of treatment, no positive ADA sample

ADA Status of a Subject:

- Baseline ADA Positive Subject: A subject with baseline ADA positive sample
- ADA Positive Subject: A subject with at least one ADA positive sample relative to baseline at any time after initiation of treatment during the defined observation time period
 1. *Persistent Positive (PP)*: ADA positive sample at 2 or more sequential time points, where the first and last ADA positive samples are at least 16 weeks apart
 2. *Not PP-Last Sample Positive*: Not persistent but ADA positive sample in the last sampling time point

3. *Other Positive*: Not persistent positive but some ADA positive samples with the last sample being negative
- ADA Negative Subject: A subject with no ADA positive sample after the initiation of treatment

